4.2.4.2 Secondary Endpoint - Efficacy

The efficacy objective of this trial is to evaluate the anti-tumor activity of pembrolizumab plus IL-2 in subjects with advanced RCC. Responses will be evaluated by RECIST 1.1. Best overall response rate (ORR) to include complete responders (CR) and partial responders (PR); disease control rate (DCR = CR+PR+stable disease, SD), and progression free survival (PFS) for patients treated with IL-2 combined with pembrolizumab will be collected and analyzed by cohort and for all treated patients. Outcomes will be compared to historical data for RCC patients treated with IL-2 or anti-PD-1 as monotherapy.

Immunotherapeutic agents may produce antitumor effects by potentiating endogenous cancer-specific immune responses which may be functionally anergic. The response patterns seen with such an approach may extend beyond the typical time course of responses seen with cytotoxic agents, and can manifest a clinical response after an initial increase in tumor burden or even the appearance of new lesions. In subjects who have initial evidence of radiological PD following a first course of treatment, it is at the discretion of the investigator whether to continue a subject on study treatment for a second treatment course. This decision should be based on the clinical judgment of the subject's overall clinical condition, including performance status, clinical symptoms, laboratory data, and tolerance for study treatments.

Subjects recommended to receive a second treatment course after PD should meet the following criteria:

- Absence of signs and symptoms indicating disease progression
- Absence of progressive tumor at critical anatomical sites (e.g., cord compression) requiring urgent alternative medical intervention
- Absence of rapid progression of disease
- No decline in ECOG performance status

This allowance takes into account the observation that some subjects can have a transient tumor flare in the first few months after the start of immunotherapy, but with subsequent disease response.

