5.2.1.2 Rules for Dose Escalation

Dose-limiting toxicities (DLT's) observed in course 1 will be used to determine escalation to the next dose level. A course is 12 weeks. The study will use a 3 + 3 trial design for IL-2 dose escalation. The first 3 patients will be enrolled at Dose Level 1. If no dose-limiting toxicities (DLT's) occur in the first 3 patients over treatment course 1, Dose Level 2 will then open for enrollment of the next 3 patients. In the absence of DLT's in three patients treated at Dose Level 2, then Dose Level 3 will open for enrollment of the next 3 patients.

If 1 of 3 subjects in a cohort experiences a DLT, the Cohort will expand to 6 pts. If only 1 of 6 patients experiences a DLT with all patients followed for safety endpoints to the end of course 1, then the next cohort dose level will open to enroll.

If two or more patients in a cohort experience a DLT, that dose level exceeds the MTD.

If two or more delayed DLT's (i.e., DLT's that occur after course 1) are noted within a dose-escalation cohort, accrual will be held pending safety analysis by the Principal Investigator and Merck and restarted only with Principal Investigator and Sponsor approvals with IRB and FDA notification.

Dose escalations or de-escalations of pembrolizumab are not allowed. Treatment delays for toxicity are allowable as described in [Section 5.2.1.4](#). Patients enrolled into Dose Level 3 who require treatment interruption and meet restarting criteria as described in [Section 5.2.1.4](#) may have IL-2 dosing de-escalated to the IV IL-2 Dose Level 2 for the subsequent treatment cycle and/or course(s) 2 and/or 3. Individual patient IL-2 dosing cannot be escalated.

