7.2.2.5 Tumor Imaging and Assessment of Disease

Tumor imaging by CT or MRI scans will be obtained at screening, at the end of each treatment course, and every 12 weeks following completion of therapy for patients who remain in Surveillance Follow-Up as specified in the Trial Flow Chart ([Section 6.0](#)). Disease status will be assessed versus baseline imaging for response category by RECIST 1.1 criteria (see Section 13.3).

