9.0 STATISTICAL ANALYSIS PLAN

9.1 Statistical Analysis Plan

The primary objective of this study is to evaluate the safety of IL-2 in combination with pembrolizumab. Statistical analysis will be descriptive for observed toxicities.

The secondary objective is to evaluate clinical outcomes (CR, PR, ORR, DCR, PFS) in comparison to historical data among advanced RCC patients treated with HD IL-2 or anti-PD1 monotherapies. The target enrollment for a conditional expansion cohort will be exploratory in nature, and no predictive statistical analysis has been applied.

Progression-free survival will be defined from the time of registration to progression or death. Patients last known to be alive and progression-free will be censored at the date of their last disease assessment. PFS will be evaluated using the method of Kaplan-Meier. Median PFS times and associated 95% confidence interval will also be calculated.

Exploratory objectives include the evaluation of the PD-1 pathway. For this objective, PD-1 pathway protein expression measures will be correlated with clinical outcomes. Specifically, the

association between pre-treatment PD-L1 expression by IHC, TIL density and T cell subset identification for CD4+, CD8+ and Treg cells, and peripheral blood analysis to quantify lymphocyte subsets including CD4+/CD8+/Treg and overall response will be compared using logistic regression. In addition, the association between end of cycle peripheral blood re-analysis to quantify lymphocyte subsets including CD4+/CD8+/Treg and PFS will be evaluated using a Cox proportional hazards model, among patients alive and progression-free at end of treatment. Similarly, the association between PD-L1 expression by IHC and TIL density and T cell subset identification for CD4+, CD8+ effector and Treg cells at the end of treatment and PFS will be evaluated among patients who do not achieve a CR but are also progression-free and the end of treatment.

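### A 95% confidence interval for median PFS cannot reach its stated level in a three-patient cohort under the Kaplan-Meier analysis planned; a minor point, fixed by limiting the interval to the pooled group

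*Combined protocol and SAP*

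**What the plan says.** Section 9.1 sets the method, "PFS will be evaluated using the method of Kaplan-Meier", and then adds: "Median PFS times and associated 95% confidence interval will also be calculated". Its censoring rule is: "Patients last known to be alive and progression-free will be censored at the date of their last disease assessment". It does not say which confidence interval for the median is meant, and it sets no minimum number of patients or events.

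Section 4.2.4.2 gives the level of analysis. Response, disease control and PFS data "will be collected and analyzed by cohort and for all treated patients".

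Section 5.2.1.2 fixes the cohort sizes. "The first 3 patients will be enrolled at Dose Level 1". Further up: "In the absence of DLT's in three patients treated at Dose Level 2, then Dose Level 3 will open for enrollment of the next 3". The larger size comes only after a dose-limiting toxicity: "If 1 of 3 subjects in a cohort experiences a DLT, the Cohort will expand to 6 pts". The trial summary in Section 1.0 gives a total of 12 to 15 patients.

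Section 7.2.2.5 times the scans "at the end of each treatment course, and every 12 weeks following completion of therapy".

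**The concern.** A confidence interval for a median that assumes no survival model can only be built from the observed times. With three of them there are few intervals to choose from, and the widest may still fall short of the stated level. If so, the by-cohort PFS output would carry a 95% label that it does not earn.

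Both Section 4.2.4.2 and Section 9.1 set outcomes against historical results for IL-2 or anti-PD-1 monotherapy. A reader making that comparison for one dose level would take the label at face value. Because the plan names no interval method, the analyst could also choose between an open and a closed upper limit after seeing the data.

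**Working it through.** **Inputs.** Confidence level 95% and Kaplan-Meier (Section 9.1); per-cohort and pooled analysis (Section 4.2.4.2); cohorts of 3, or 6 after one DLT in 3 (Section 5.2.1.2); total 12 to 15 (Section 1.0). Two-sidedness is assumed, as the plan does not state it. The plan offers no precision calculation to reproduce, so the check is whether 95% is attainable.

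**1. Exact coverage, continuous and uncensored times.** Each patient's time falls below the true median with probability 1/2. With n patients:

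- First event to last event misses only if all times lie on one side: coverage = 1 − 2(1/2)^n.
- First event to no upper limit misses only if all times lie above the median: coverage = 1 − (1/2)^n.

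| n | first to last event | first event, no upper limit |
|---|---|---|
| 3 | 1 − 2/8 = 75.0% | 1 − 1/8 = 87.5% |
| 4 | 87.5% | 93.8% |
| 5 | 93.8% | 96.9% |
| 6 | 96.9% | 98.4% |

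At n = 3 neither reaches 95%. A closed interval first does so at n = 6, an open one at n = 5.

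**2. What the usual Kaplan-Meier interval gives at n = 3.** It keeps the times at which the confidence limits for survival bracket 0.5.

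- After the first event, S = 2/3 and the Greenwood sum is 1/(3×2) = 0.167. The lower limit for S is 0.054 on the log-log scale (0.133 plain, 0.300 log). All are below 0.5, so the lower limit for the median is the first event.
- After the second event, S = 1/3 and the sum is 0.167 + 1/(2×1) = 0.667. The upper limit for S is 0.774 log-log (0.867 plain, above 1 log). All exceed 0.5.
- After the third event, S = 0 and the limits are undefined.

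The upper limit for the median is therefore never reached on any of the three scales, and coverage is the open-ended 87.5%. Simulation (20,000 exponential samples per scale) gave 87.5% to 87.6%, with no upper limit in any sample. The 75% applies only if the analyst closes the interval at the last event.

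**3. Censoring.** With exponential times and about 25% of patients independently censored, simulated log-log coverage at n = 3 is about 85% open and about 68% closed. Under the closed convention about 25% of intervals still have no upper limit.

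**4. Ties at scans.** If progression is recorded at only three scan times, closed coverage at n = 3 is 1 − p1³ − p3³, where p1 and p3 are the assumed shares at the first and third scans:

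- 25/50/25%: 1 − 0.0156 − 0.0156 = 96.9%
- 30/40/30%: 1 − 0.027 − 0.027 = 94.6%
- 40/20/40%: 1 − 0.064 − 0.064 = 87.2%

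**5. Pooled group.** Order-statistic intervals reach 95%: third to tenth event of 12 gives 96.1%, and fourth to twelfth of 15 gives 96.5%. The method matters. Simulated uncensored coverage of the nominal 95% Kaplan-Meier interval at n = 12 is 85.3% plain, 92.6% log and 97.8% log-log; at n = 15 it is 88.3%, 93.6% and 93.7%.

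**6. How often a three-patient cohort arises.** With all three levels filled by 3 or 6 patients, 12 = 3 + 3 + 6 and 15 = 3 + 6 + 6. At least one cohort has three patients. If escalation stops early this need not hold.

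**The case against.** The strongest reply is that the sentence on the 95% interval does not mention cohorts. The plan could be met by listing PFS per cohort and giving the median and interval only for the pooled group, where 95% is attainable. That is a fair reading. But nothing in the plan makes that restriction, and the interval sentence is the only numerical PFS summary in Section 9.1. Joining it to the per-cohort analysis in Section 4.2.4.2 is a natural inference, though not an explicit instruction.

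Three stronger readings are tempting and are not supported.

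- A reader might infer that cohort error bars would be far too narrow. That would need the interval to be closed at the last event, a convention the plan does not state. The usual interval is open-ended and visibly uninformative, not falsely precise.
- A reader might infer that no 95% interval of any kind exists for three patients. The limit applies to distribution-free intervals. An exponential model with three events holds about 95% if the model is true (simulated 94.9%, upper limit about 11.7 times the lower), but the plan names no such model.
- A reader might infer that dose levels would be wrongly ranked on PFS. The plan compares with historical data only; it contains no comparison of PFS between dose levels.

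It is also fair to say that nothing operational depends on the interval. Escalation rests on DLTs in course 1, and PFS is a secondary endpoint of a phase I safety trial. That limits the importance of the point without removing it.

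**Conclusion.** The point holds as a minor reporting defect. For three-patient cohorts the 95% label would be wrong: coverage is 87.5% for the usual Kaplan-Meier interval, with its upper limit never reached, and 75% if the interval is closed at the last event. These figures are exact for continuous, uncensored times. The censored figures assume exponential times and independent censoring. Ties at 12-week scans can move coverage either close to the stated level or well below it, depending on the pattern.

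The conclusion rests on reading Sections 9.1 and 4.2.4.2 together. It does not extend to the pooled group. A six-patient cohort can reach 96.9% without censoring, but only by using the whole range of its times.

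**What to change.** In Sections 9.1 and 4.2.4.2, state that the Kaplan-Meier median with its 95% interval is given for all treated patients pooled, and name the interval method, including how the upper limit is handled when the curve reaches zero. For each dose-level cohort, list the individual PFS times, marking censored ones, and the number progression-free at the scheduled scans at the end of courses 1, 2 and 3 (weeks 12, 24 and 36).

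The cost is a sentence or two in the plan. The scans are already scheduled, so no new data are needed. The downside is that no cohort-level median is quoted; in a cohort of three it would be only the middle observed time, which the listing already shows.

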3.3 Exploratory Objectives

- To investigate the association of PD-L1 protein expression by pretreatment tumor with response to treatment.
- To investigate the association of regulatory T cell (Treg) frequency and Treg to effector T cell (Teff) ratios in peripheral blood and tumor tissue with response to therapy.
- To investigate the association of *de novo* serological and cellular responses against the ubiquitous RCC tumor antigen 5T4 with response to therapy.
- To investigate the association of tumor infiltrating lymphocyte (TIL) repertoire clonality with response to therapy and to assess the detection of dominant TIL clones within peripheral blood over time in responding patients.
- To investigate the association of whole genome copy number alterations measured on pretreatment archived, formalin fixed, paraffin embedded (FFPE) tumor with response to therapy.

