The expression of PD-1 pathway proteins has been extensively studied in RCC tumors and shown to closely associate with RCC progression and poor disease specific outcomes. In the largest reported series of 306 clear cell RCC tumors, Thompson and co-workers analyzed PD-L1 expression by immunostaining formalin-fixed paraffin-embedded (FFPE) tissue samples. Tumor cell membranous expression of PD-L1 (with a threshold of $\geq 5\%$ of tumor cells stained with mAb 5H1) was seen in 24% of samples and strongly associated with cancer-specific death (risk ratio (RR) 3.92; $P < 0.001$). This association also remained significant in multivariate modeling (RR 2.0, $P=0.003$) [32]. PD-1 expression by tumor-infiltrating lymphocytes has also been analyzed in both fresh-frozen or FFPE clear cell RCC tissue. High PD-1 expression associated with distant metastatic relapse, and inferior relapse-free and overall survival versus the PD-1-negative patient subset [33, 34].

The recognition of advanced RCC as a tumor responsive to immunotherapy together with evidence for a PD-1/PD-L1 mediated immune escape mechanism operating in RCC tumors has provided a compelling rationale for initial testing of blocking antibodies specific for PD-1 or PD-L1 in patients with advanced RCC. Nivolumab, a fully human IgG4 mAb specific for human PD-1 was tested in a dose escalation format in 296 patients that included 34 patients with advanced clear cell RCC treated at 1 or 10 mg/kg every 2 weeks [35]. In this heavily pre-treated cohort, significant anti-tumor activity was observed with an ORR of 27% and median duration of response 12.9 months. Treatment was judged to be generally well tolerated and no MTD was reached. Grade 3/4 treatment related adverse events were observed in 14% of patients and there were 3 drug-related deaths due to pneumonitis, however none in the RCC cohort [35]. In a phase II study, nivolumab was further studied in 168 RCC patients randomized to nivolumab at 0.3, 2

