or 10 mg/kg every 3 weeks. ORR by treatment group was 20%, 22% and 20% respectively and the overall rate of treatment related AE's was 11%. There were no high-grade pneumonitis events and no treatment related deaths. There was no dose-response relationship detected for ORR, PFS, or incidence of treatment-related AE's [36]. A phase III study of nivolumab (Checkmate 025) enrolled 821 RCC patients who had failed 1 to 3 lines of prior therapy including antiangiogenic treatment targeting the VEGF pathway. Nivolumab given at 3 mg/kg every 2 weeks was compared to everolimus in 1:1 randomization. Median overall survival favored nivolumab (HR 0.73, P=0.002) and the survival benefit for nivolumab treatment was seen independent of tumor expression of PD-L1. The ORR determined by RECIST 1.1 was also superior for nivolumab (25% vs 5%). There were no nivolumab associated deaths, and the incidence of grade 3/4 treatment-related AE's was lower with nivolumab than everolimus (19% vs 37%). [37]

Two blocking mAb's targeting PD-L1 have also reported results from phase I clinical trials that included patients with advanced RCC. Both BMS-936559 and MPDL3280A were judged to be well tolerated and demonstrated ORR's of 12% and 14% respectively in heavily pre-treated RCC patients [38, 39].

Taken together, the emerging data with blocking antibodies targeting PD1 or PD-L1 demonstrating spontaneous and durable regressions for a subset of treatment-refractory RCC tumors suggests the PD-1 pathway represents a dominant control point for the regulation of tumor-reactive T cell responses.

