4.1.4 Preclinical and Clinical Trial Data for Pembrolizumab

Pembrolizumab is a potent and highly selective humanized monoclonal antibody (mAb) of the IgG4/kappa isotype designed to directly block the interaction between PD-1 and its ligands, PD-L1 and PD-L2. Pembrolizumab has been studied in an open-label, single-arm, phase 2 trial (Keynote 427) as first-line, single-agent therapy for RCC patients with both clear cell (cohort A; N=110) and non-clear cell histology (cohort B; N=165) [40, 41]. With a median follow up of 18.5 months, patients treated in Cohort A had a confirmed ORR of 36% and a median OS that has not been reached. The incidence of grade 3-5 treatment-related AE's was 29% [40]. Refer to the Investigator's Brochure for additional pembrolizumab preclinical and clinical data.

Keytruda™ (pembrolizumab) is approved in the United States for the treatment of patients with advanced RCC (in combination with axitinib) and 14 additional cancer indications.

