The anti-PDL1 antibody avelumab has also been studied in combination with axitinib in the front-line setting in a randomized phase 3 trial enrolling 886 patients with advanced clear cell RCC (Javelin 101). In the primary analysis population of 560 patients with PD-L1-positive tumors (63.2%), the median progression-free survival was 13.8 months with avelumab–axitinib versus 7.2 months with sunitinib (hazard ratio for disease progression or death, 0.61, $P<0.001$); and the ORR was 55.2% with avelumab plus axitinib versus 25.5% with sunitinib. In the overall population, the median PFS for pembrolizumab–axitinib was 13.8 months, as compared with 8.4 months for sunitinib (hazard ratio, 0.69, $P<0.001$) and PFS favored pembrolizumab–axitinib across all IMDC risk groups. Grade ≥ 3 treatment-related adverse events occurred in 56.7% of avelumab–axitinib treated patients versus and 55.4% of sunitinib treated patients [44]. Based on these data, avelumab plus axitinib received FDA-approval in May 2019 for first-line treatment of patients with advanced RCC.

In summary, treatment regimens containing blocking antibodies targeting PD1, CTLA-4 or PDL1 are now firmly established as front-line standard of care treatment options for most patients with advanced RCC.

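### SAP 9.1 relates about eight biomarkers to response by logistic regression in 12 to 15 patients, without saying whether they are fitted singly or jointly and without an estimator suited to that size

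*Combined protocol and SAP*

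**What the plan says.** SAP 9.1 introduces this part of the analysis with "Exploratory objectives include the evaluation of the PD-1 pathway". It lists pre-treatment PD-L1 by IHC, TIL density, tumour CD4+, CD8+ and Treg cells, and blood CD4+, CD8+ and Treg cells. Their association "and overall response will be compared using logistic regression". That is five tumour and at least three blood measures, so about eight.

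The models serve Section 3.3, whose first item is "To investigate the association of PD-L1 protein expression by pretreatment tumor with response to treatment"; the second concerns Treg frequency and Treg:Teff ratios. Section 1.0 gives 12 to 15 subjects. Under Section 2.3, opening an expansion cohort and changing the enrolment target would need a protocol amendment.

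Section 9.1 does not state whether markers enter singly or together, how PD-L1 is scaled, which estimator or interval is used, or what is reported if no finite odds ratio exists. The only interval it mentions is for PFS: "Median PFS times and associated 95% confidence interval will also be calculated".

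**The concern.** A logistic model has no finite maximum-likelihood estimate when a marker, or a linear combination of markers, separates responders from non-responders. The Wald interval is then unusable, and the profile-likelihood interval keeps only one finite bound. With 12 to 15 patients this is a practical possibility, and it becomes more likely as the marker becomes stronger. With eight markers in one model it is close to certain.

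What is at stake is whether an odds ratio and interval can be reported for the PD-L1 and Treg objectives, and how far the interval can be trusted. As written, both depend on an unstated modelling choice and a software default.

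**Working it through.** The plan gives no power, precision or error rate for these models, so it has no figure of its own to reproduce.

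**Inputs.** n = 12 and 15 (Section 1.0). Response rates are scenarios taken from the background, not planning values: 21% for high-dose IL-2 (4.1.2), 25% for nivolumab in phase III (4.1.3), 36% for first-line pembrolizumab (4.1.4), and 77% for pembrolizumab plus high-dose IL-2 at one centre (4.2.1). The 95% level is borrowed from the PFS sentence.

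**1. One continuous marker unrelated to response (exact).** Given k responders of n, with 0 < k < n, all responders lie above or all lie below the non-responders with probability 2/C(n,k). Add the trials with no responders or only responders. With q = 1 − p:

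P(no finite estimate) = pⁿ + qⁿ + Σ Bin(k; n, p) × 2/C(n,k) = pⁿ + qⁿ + 2pq(qⁿ⁻¹ − pⁿ⁻¹)/(q − p).

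For n = 12 and p = 0.36:
- no or only responders: 0.64¹² + 0.36¹² = 0.0047;
- separation: 2 × 0.2304 × (0.64¹¹ − 0.36¹¹)/0.28 = 0.0121;
- total: 0.0168.

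**2. One continuous marker related to response (simulation, 4,000 trials per setting).** Response is Bernoulli at the stated rate. The marker is normal with SD 1 in each group, and the group means differ by d SD, so the logistic model holds with log odds ratio d per SD. Percentage of trials with no finite estimate:

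| n | response rate | d = 0 (exact) | d = 1 | d = 1.5 | d = 2 |
|---|---|---|---|---|---|
| 12 | 25% | 6.3 | 14.0 | 25.7 | 43.3 |
| 12 | 36% | 1.7 | 7.5 | 17.3 | 34.4 |
| 12 | 77% | 8.0 | 15.2 | 28.2 | 44.0 |
| 15 | 25% | 2.7 | 7.6 | 15.7 | 32.2 |
| 15 | 36% | 0.4 | 2.7 | 9.2 | 22.7 |
| 15 | 77% | 3.7 | 8.5 | 19.0 | 33.5 |

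A different set-up, with odds ratios of 3 to 10 per SD of the whole sample and the intercept set at 36%, gave 6-21% at n = 12 and 2-12% at n = 15. The direction is the same; the level depends on how effect size is defined.

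**3. Eight markers in one model.** Linear-programming check for separation, 1,500 trials per setting, eight markers unrelated to response, rates 21% / 36% / 77%:
- n = 12: 99.1% / 97.5% / 99.0%;
- n = 15: 93.4% / 83.7% / 92.2%.

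As a cross-check at a 50% response rate, Cover's formula 2 Σₖ₌₀⁸ C(n−1,k)/2ⁿ gives 96.7% and 78.8%. Correlation among continuous markers does not change this null probability, because separability is unaffected by invertible linear transformation of the markers.

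**4. Coverage of 95% intervals, single marker.** d = 0, 1, 2, 800 trials per setting, counting trials in which a model can be fitted:
- maximum-likelihood profile: 82-93%; a repeat run gave about 81-91%, hence 81-93% overall;
- Firth profile penalised likelihood: about 95-98%;
- Wald: 94-100%, but only among trials with a finite estimate.

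Simulation standard error near 85% is √(0.85 × 0.15/800) = 0.013. Both ends of the Firth interval were finite in all 170 separated trials checked.

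**5. Cost of the penalty.** The median Firth slope was 0.80-0.89 when the true value was 1 (11-20% low) and 1.43-1.61 when it was 2 (20-29% low).

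**6. Illustration with invented data.** n = 12, 4 responders, 3 PD-L1-positive patients, all responding. Ordinary maximum likelihood drifts to a log odds ratio of 23.6 with standard error about 16,900. For a 2×2 table the Firth estimate equals adding 0.5 to each cell: (3.5 × 8.5)/(0.5 × 1.5) = 39.7. A Wald interval around it runs from 1.3 to 1230, so the result can be reported but remains very imprecise.

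**The case against.** The strongest reply is that this is a thin specification, not an error. The analysis is exploratory, in a Phase I trial whose primary analysis is descriptive. The phrase logistic regression does not exclude penalised or exact versions. For one continuous marker with no association, failure is uncommon, and 28-54% of those failures are trials with no or only responders, where Firth regression would not help either. The larger single-marker figures need an assumed 1.5-2 SD effect. All of this stands and is why the point is minor. It does not remove the joint-model ambiguity or the under-coverage of the default profile interval.

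A reader might infer more than the documents support:

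- **That the planned tests have the wrong size or poor power.** SAP 9.1 states no significance level, test or decision for these models, so such figures would describe an analysis that is not planned.
- **That PD-L1 will be dichotomised and so often give an empty cell.** With no association, an empty cell or margin would arise in 16-61% of trials. That needs a cut the SAP does not state and positivity rates borrowed from elsewhere in the background: 24% from a tumour series (4.1.3) and 63.2% from an avelumab trial (4.1.5).
- **That a joint eight-marker model is planned.** The wording permits it but does not say so.

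It is also fair to object that offering Firth or exact methods as alternatives would leave the choice open again. The fix therefore names one.

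**Conclusion.** The point holds as a minor, inexpensive improvement. SAP 9.1 leaves open whether about eight markers are fitted singly or jointly and names no estimator suited to 12 to 15 patients. Under ordinary maximum likelihood the chance of no finite estimate is about 84-99% for a joint model. For a single continuous marker it is about 0.4-8% with no association and about 9-44% at 1.5-2 SD. The 95% profile-likelihood interval covers about 81-93%.

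These figures assume normal continuous markers, response rates taken from the background sections, and complete marker and response data in 12 or 15 patients. Missing tissue would make matters worse. The 3+3 rules allow 9 to 18 patients if all three levels open (three levels of 3 or 6), so the achieved number may fall outside 12 to 15.

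The finding does not mean that the biomarker analysis is invalid as written, or that a better estimator would make it informative. Dose escalation, safety and the primary objective are unaffected. The Cox models in the same section were not assessed here.

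**What to change.** Add to SAP 9.1:

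- Each marker is analysed in its own model by Firth-penalised logistic regression, reported as an odds ratio with a 95% profile penalised-likelihood interval.
- PD-L1 is analysed on one scale, fixed before response data are examined.
- If there are no responders or only responders, or if a marker takes one value in all patients, marker distributions are described and no model is fitted.
- Estimates are exploratory and not adjusted for multiplicity.

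The cost is SAP wording only, with the same patients and data and standard software. The downside is shrinkage of log odds ratios (median about 11-29% low at 1-2 SD) and slightly conservative intervals. Precision and power stay poor at this sample size.
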